4. STUDY OBJECTIVES

4.1 Primary

To evaluate the PK of insulin lispro following administration of a single 15-U subcutaneous (SC) dose of LY900014 compared to insulin lispro (Humalog) within each type 1 diabetes mellitus (T1DM) population (elderly and younger adults).

4.2 Secondary

To compare the GD during a euglycaemic clamp of LY900014 and insulin lispro (Humalog) following administration of a single 15-U SC dose in elderly and younger adults with T1DM.

To evaluate the safety and tolerability of the novel LY900014 formulation.

[figure not shown]
4.3 Exploratory

To evaluate whether the difference between LY900014 and insulin lispro in PK and PD parameters is similar between elderly and younger adults.

5. STUDY DESIGN

This is a Phase 1, randomized, patient- and investigator-blind, 2-treatment, 2-period, crossover study that compares the PK and GD of insulin lispro from LY900014 and insulin lispro (Humalog) following administration of a single 15-U SC dose in elderly and younger adults with T1DM who are either on multiple daily insulin injections or on continuous subcutaneous insulin infusion (CSII) via a sponsor-approved insulin pump. Study ITRR will be conducted at 1 or more sites.

Figure 1 illustrates the study design.

Abbreviations: CRU = clinical research unit; ED = early discontinuation; SC = subcutaneous; T1DM = type 1 diabetes mellitus

Figure 1. Illustration of study design

Patients will be randomized to 1 of 2 treatment sequences according to the actual randomization table provided to the site. Each patient will participate in a screening visit, 2 clinical research unit (CRU) inpatient dosing visits, and a follow-up visit. Before each dose, a run-in period of 1 to 6 hours to stabilize blood glucose will occur. Dosing visits will be separated by a wash-out period of 3 to 15 days, during which patients will resume their normal insulin treatment with the exemption of the insulin switch 48 to 72 hours prior to dosing as described in the protocol. At each visit, patients will receive either LY900014 or insulin lispro and undergo a euglycaemic clamp procedure where the time-concentration and time-action profiles of the study treatment will be evaluated simultaneously for up to 10 hours using an automated clamp device. Briefly, the aim of the euglycaemic clamp is to maintain euglycaemia after the administration of a dose of insulin by means of variable glucose infusion. The variable glucose infusion maintains or “clamps” glucose at a constant euglycaemic target; therefore, the glucose infusion rate (GIR) reflects the GD effect of the insulin.

All patients will be instructed to perform at least 4-point daily self-monitoring plasma glucose (SMPG), as well as continue their short-acting insulin during lead-in. The SMPG and prandial insulin doses should be recorded in the patient’s diary, which will serve as a source document.

6. TREATMENTS

The following is a list of the study treatment and age group names that will be used in the TFLs.

Study Treatment Name	Treatment order in TFL
LY900014	1
Humalog	2
Age Group Name	Age Group order in TFL
Elderly adults	1
Younger adults	2

7. SAMPLE SIZE JUSTIFICATION

Up to 42 younger adult and 42 elderly patients may be enrolled to ensure that at least 34 patients in each age group complete the study. Thirty-four completing patients in each age group will provide approximately 95% power to demonstrate a 40% increase in the insulin lispro area under the plasma concentration-time curve from time zero to 30 minutes (AUC[0-30min]) between LY900014 and Humalog within each age group. Testing will be done at an alpha level of 0.05 with a 2-sided confidence interval (CI). The variability was estimated by analyzing a Lilly internal study that showed a log-scale standard deviation of within-patient difference in AUC(0-30min) of 0.5. Analysis of internal data showed a log-scale standard deviation of within patient difference in time to early half-maximal plasma concentration (early 50% t_{max}) of 0.5,

which provides approximately 95% power to show a 30% reduction in early 50% t_{max} , testing with an alpha level of 0.05 and a 2-sided CI.

In addition, the study is adequately powered to evaluate the GD parameters within each age group. There is approximately 80% power to detect a 20% decrease in both time to onset of insulin action (T_{onset}) and time to half-maximal GIR before TR_{max} (early 50% TR_{max}), and approximately 85% power to detect at least a 40% increase in total amount of glucose infused over 30 minutes ($G_{tot}[0-30min]$) and total amount of glucose infused over 1 hour ($G_{tot}[0-1h]$).

8. DEFINITION OF ANALYSIS POPULATIONS

The “Safety” population will consist of all patients who received at least one dose of study drug.

The primary statistical analyses for PK will be conducted on those patients who receive at least 1 dose of study drug and have measurable insulin lispro concentrations.

The primary statistical analysis for GD will be conducted on those patients who complete at least 1 clamp procedure.

Supportive analyses will be done on the key PK and GD parameters for the patients who complete all treatment periods with evaluable data.

All protocol deviations that occur during the study will be considered for their severity/impact and will be taken into consideration when patients are assigned to analysis populations.

9. STATISTICAL METHODOLOGY

9.1 General

Data listings will be provided for all data that is databased. Summary statistics and statistical analysis will only be presented for data where detailed in this SAP. For continuous data, summary statistics will include the arithmetic mean, arithmetic standard deviation (SD), median, min, max and N; for log-normal data (e.g. the PK parameters: AUCs and C_{max}) the geometric mean and geometric coefficient of variation (CV%) will also be presented. For categorical data, frequency count and percentages will be presented. Data listings will be provided for all patients up to the point of withdrawal, with any patients excluded from the relevant population highlighted. Summary statistics and statistical analyses will generally only be performed for patients included in the relevant analysis population. For the calculation of summary statistics and statistical analysis, unrounded data will be used.

Mean change from baseline is the mean of all individual patients' change from baseline values. Each individual change from baseline will be calculated by subtracting the individual patient's baseline value from the value at the timepoint. The individual patient's change from baseline values will be used to calculate the mean change from baseline using a SAS procedure such as Proc Univariate.

Data analysis will be performed using [REDACTED] or greater.

9.2 Demographics and Patient Disposition

Patient disposition will be listed. The demographic variables age, sex, race, ethnicity, country of enrolment, site ID, hip and waist circumference, body weight, height and body mass index will be summarized by age group and listed. In addition, screening HbA1c, fasting blood glucose, fasting C-peptide, previous insulin therapy (basal and prandial) and duration of T1DM will be summarized and listed.

Alcohol consumption will be reported in the SDTMs in units of alcohol and will be converted to grams for the TFLs, where 1 unit is equal to 8 grams of pure alcohol.

9.3 Pharmacokinetic Assessment

9.3.1 Pharmacokinetic Parameter Estimation

Patients who receive at least 1 dose of study drug and have measurable insulin lispro concentrations will be included in the PK analysis dataset.

PK analyses will be conducted using standard noncompartmental methods of analysis using CCI on a computer that meets or exceeds the minimum system requirements for these programs. The version of any software used for the analysis will be documented and the program will meet the Lilly requirements of software validation. It is possible that other validated equivalent PK software programs may be utilized if appropriate, warranted, and approved by global PK management.

Free serum insulin lispro concentrations will be used to calculate several PK parameters, including early 50% t_{max} , time to late half-maximal plasma concentration (late 50% t_{max}), maximum observed concentration (C_{max}), t_{max} , $t_{1/2}$, and area under the plasma concentration-time curve from time zero to the last recorded time, AUC(0-30min), area under the plasma concentration-time curve from time zero to 1 hour, area under the plasma concentration-time curve from time zero to 10 hours, and area under the plasma concentration-time curve from time zero to infinity. Other parameters may be calculated as deemed appropriate. Additional partial area under the plasma concentration-time curves (AUCs) may be computed as necessary. The primary insulin lispro PK parameters for faster insulin lispro absorption analysis are early 50% t_{max} and AUC(0-30min).

Given the predicted low systemic concentrations of treprostinil, the PK analysis of treprostinil from the LY900014 dosing will be conducted using the available data. The primary analysis of the treprostinil concentrations will be focused on assessing time to maximum concentration (t_{max}) and C_{max} .

Although attempts will be made to adhere to the scheduled collection times (Section 2 of the protocol), it is recognized that situations arise that may compromise the scheduled times. Parameters will be individually calculated for each patient based on actual collection times and presented using summary statistics.

9.3.2 Pharmacokinetic Statistical Inference

Log-transformed C_{max} , AUC(0-30min), AUC(0-1h), AUC(0-10h), AUC(2-10h), AUC(0- t_{last}), AUC(0-inf), CL/F and V_z/F for insulin lispro will be evaluated to estimate least-squares geometric means, ratios of geometric means between LY900014 and Humalog (reference), and their corresponding 95% CIs for each age group separately using the statistical model that includes treatment, sequence, and period as fixed effects and patient within sequence as a random effect.

Example SAS code:

```
proc mixed data=pk;
class patient period treatment sequence ;
model logpk = treatment period sequence / ddfm=kr;
random patient(sequence);
lsmeans treatment;
run;
```

The same model without log-transformation will be used for the analysis of the PK time parameters (early 50% t_{max} , late 50% t_{max} , t_{max} , and $t_{1/2}$). Least-squares means, treatment differences in least-squares means, and the corresponding 95% CIs for the treatment differences will be estimated from the model. The treatment ratios and 95% CIs for the ratios will be calculated using Fieller's Theorem (Chow and Liu 2009³).

All analyses will be repeated for the population of patients who complete the study.

An exploratory analysis on the interaction between treatment and age group will be assessed using data from both age groups by a model similar to that for each age group, with the addition of age group and the interaction of treatment by age group as fixed effects. This test will be used to compare whether the LY900014 versus insulin lispro treatment effect is similar between the elderly and younger adult groups. The analysis will include all PK parameters analysed previously (both untransformed and log-transformed PK parameters).

Example SAS code:

```
proc mixed data=pk;
class patient period treatment sequence agegrp;
model logpk = treatment period sequence agegrp agegrp*treatment /
ddfm=kr;
random patient(sequence);
lsmeans agegrp*treatment;
run;
```

As treprostinil plasma concentrations after administration of LY900014 are expected to be very low, a descriptive statistical analysis may be conducted if sufficient data are available for this analysis.

9.4 Glucodynamic Assessment

9.4.1 Glucodynamic Parameter Estimation

GD assessments will be determined from the glucose clamp procedure, where the GIR over time will be used as a measure of insulin effect. GD analyses will be conducted on those patients who complete at least 1 clamp procedure. A locally weighted scatterplot smoothing (LOESS) function will be applied to all individual GIR versus time profiles in each treatment group and age group using CCI

The fitted data for each patient will be used to calculate the following GD parameters: T_{onset} , maximum GIR (R_{max}), time to R_{max} (TR_{max}), early 50% TR_{max} , time to half-maximal GIR after TR_{max} (late 50% TR_{max}), total amount of glucose infused (G_{tot}), $G_{\text{tot}}(0-30\text{min})$, and $G_{\text{tot}}(0-1\text{h})$. Additional partial glucose AUCs, such as total amount of glucose infused over 2 hours, may be computed as necessary. The values of these GD parameters will be summarized by treatment group and age group through descriptive statistics. Mean LOESS fits of GIR versus time profiles will be generated. The primary GD parameters for analysis are early 50% TR_{max} , $G_{\text{tot}}(0-30\text{min})$, $G_{\text{tot}}(0-1\text{h})$, and T_{onset} .

9.4.2 Glucodynamic Statistical Inference

The GD parameters will be listed and summarized by treatment and age group.

The statistical model will be the same as the model used for the analysis of the PK parameters. The non-time variables will be log-transformed prior to analysis and will include R_{max} , G_{tot} , $G_{\text{tot}}(0-30\text{min})$, $G_{\text{tot}}(0-1\text{h})$, and $G_{\text{tot}}(0-10\text{h})$. For GD parameters that have at least 1 patient with a value equal to zero, a value equal to the smallest non-zero observed GD value for that parameter divided by 2 will be added to all values, and the analysis of the log-transformed data will be performed.

The same model without log-transformation will be used for the analysis of the GD time parameters (T_{onset} , TR_{max} , early 50% TR_{max} , and late 50% TR_{max}). Least-squares means, treatment differences in least-squares means, and the corresponding 95% CIs for the treatment differences will be estimated from the model. The treatment ratios and 95% CIs for the ratios will be calculated using Fieller's Theorem

All analyses will be repeated for the population of patients who complete the study.

An exploratory analysis on the interaction between treatment and age group will be assessed using data from both age groups by a model similar to that for each age group, with the addition of age group and the interaction of treatment by age group as fixed effects. This test will be used to compare whether the LY90014 versus insulin lispro treatment effect is similar between the elderly and younger adult groups. The analysis will include all GD parameters analysed previously (both untransformed and log-transformed GD parameters).

9.5 Safety and Tolerability Assessments

9.5.1 Adverse events

Where changes in severity are recorded in the Case Report Form (CRF), each separate severity of the adverse event (AE) will be reported in the listings, only the most severe will be used in the summary tables. A pre-existing condition is defined as an AE that starts before the patient has provided written informed consent and is ongoing at consent. A non-treatment emergent AE is defined as an AE which starts after informed consent but prior to dosing. A treatment-emergent AE is defined as an AE which occurs postdose or which is present prior to dosing and becomes more severe postdose.

All AEs will be listed. Treatment-emergent AEs will be summarized by treatment, age group, severity and relationship to the study drug. The frequency (the number of adverse events, the number of patients experiencing an adverse event and the percentage of patients experiencing an adverse event) of treatment-emergent adverse events will be summarized by treatment, age group, Medical Dictionary for Regulatory Activities (MedDRA) version 19.1 system organ class and preferred term. The summary and frequency adverse event tables will be presented for all causalities and those considered related to the study drug. Any serious adverse events will be tabulated.

9.5.2 Concomitant medication

Concomitant medication will be coded using the WHO drug dictionary (Version September 2016). Concomitant medication will be listed.

9.5.3 Clinical laboratory parameters

All clinical chemistry, hematology and urinalysis data will listed. Additionally clinical chemistry, hematology and urinalysis data outside the reference ranges will be listed.

Values for any clinical chemistry, hematology and urinalysis values outside the reference ranges will be flagged on the individual patient data listings.

9.5.4 Vital signs

Vital signs data will be summarized by treatment and age group, together with changes from baseline, where baseline is defined as predose of Day 1.

Furthermore, values for individual patients will be listed.

9.5.5 Electrocardiogram (ECG)

ECG data will be listed for individual patients.

9.5.6 Blood Glucose Monitoring and Hypoglycemia

Hypoglycemic events will be appropriately recorded in the CRF. In the case of a hypoglycemic event, the actual blood glucose value, if measured, will be recorded in the CRF, together with any treatments administered. Each category of hypoglycemic events (defined below) will be listed and summarized by treatment and age group.

Hypoglycemia is defined as follows:

• **Documented Hypoglycemia:**

o Documented symptomatic hypoglycemia: An event during which typical symptoms of hypoglycemia are accompanied by plasma glucose (PG) ≤ 70 mg/dL (≤ 3.9 mmol/L).

o Asymptomatic hypoglycemia: An event not accompanied by typical symptoms of hypoglycemia but with PG ≤ 70 mg/dL (≤ 3.9 mmol/L).

• **Unspecified hypoglycemia:** An event during which PG ≤ 70 mg/dL (≤ 3.9 mmol/L) but no information relative to symptoms of hypoglycemia was recorded

• **Probable symptomatic hypoglycemia:** An event during which symptoms indicative of hypoglycemia are not accompanied by a PG determination (but that was presumably caused by PG ≤ 70 mg/dL [≤ 3.9 mmol/L]).

• **Severe hypoglycemia:** An event requiring assistance of another person to actively administer carbohydrate, glucagon, or other resuscitative actions.

• **Nocturnal hypoglycemia:** Any hypoglycemic event (documented symptomatic, asymptomatic, probable symptomatic or severe hypoglycemia) that occurs between bedtime and waking.

• **Overall hypoglycemia:** This optional category combines all cases of hypoglycemia. If an event of hypoglycemia falls into multiple subcategories, the event is only counted once in this category.

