## 5. Study Design

### 5.1. Overall Design

This is a Phase 1, randomized, subject- and investigator-blind, 2-treatment, 2-period, crossover study that compares the PK and GD of insulin lispro from LY900014 and insulin lispro (Humalog) following administration of a single 15-U SC dose in elderly and younger adults with T1DM who are either on multiple daily insulin injections or on CSII via a sponsor-approved insulin pump. Study ITRR will be conducted at 1 or more sites.

Figure ITRR.1 illustrates the study design.

Subjects will be randomized to 1 of 2 treatment sequences according to the actual randomization table provided to the site. Each subject will participate in a screening visit, 2 clinical research unit (CRU) inpatient dosing visits, and a follow-up visit. Before each dose, a run-in period of 1 to 6 hours to stabilize blood glucose will occur. Dosing visits will be separated by a wash-out period of 3 to 15 days, during which subjects will resume their normal insulin treatment with the exemption of the insulin switch 48 to 72 hours prior to dosing as mentioned below. At each visit, subjects will receive either LY900014 or insulin lispro and undergo a euglycaemic clamp procedure where the time-concentration and time-action profiles of the study treatment will be evaluated simultaneously for up to 10 hours using an automated clamp device. Briefly, the aim of the euglycaemic clamp is to maintain euglycaemia after the administration of a dose of insulin by means of variable glucose infusion. The variable glucose infusion maintains or “clamps” glucose at a constant euglycaemic target; therefore, the glucose infusion rate (GIR) reflects the GD effect of the insulin.

Prior to each dosing visit, subjects with T1DM on multiple daily insulin injections have to discontinue their basal insulin, according to the following guidance:

- For subjects using insulin degludec or insulin glargine U300, the last injection of insulin degludec should occur no later than 72 hours prior to dosing.
- For subjects using insulin detemir or glargine, the last injection of insulin detemir or glargine should occur no later than 48 hours prior to dosing.
- For subjects using neutral protamine Hagedorn (NPH) insulin or other intermediate-acting insulin, the last injection of NPH insulin or other intermediate-acting insulin should occur no later than 24 hours prior to dosing.

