### **5.1.1. Inpatient Dosing Visits**

[figure not shown]
The patient will check into the CRU on Day -1 of each period in the early evening (at approximately 1700 hours). Subjects on multiple daily insulin injections would have discontinued their basal insulin but subjects using pump therapy (CSII) should arrive at the CRU with their basal rate running. All subjects will receive short-acting insulin either via an injection or via a bolus dose from the insulin pump before the start of a standardized dinner within the CRU. This prandial dose should be administered no later than 6 hours prior to the planned study drug dosing the next day. After dinner (at approximately 2200 hours), the subject is required to fast until the completion of the clamp procedure the following day. Consumption of food or beverages other than water later than approximately 2200 hours on the evening before dosing is not allowed, with the exception of minor intake of rapidly absorbable carbohydrates (not more than 20 g) if necessary to prevent hypoglycaemia (if carbohydrates have been ingested, subjects' blood glucose measurement will have to confirm that they are not hypoglycaemic). If hypoglycaemia (blood glucose level  $\leq 3.5$  mmol/L [ $\leq 63$  mg/dL] or plasma glucose  $\leq 3.9$  mmol/L [ $\leq 70$  mg/dL]) or more than 20 g of carbohydrates are needed to prevent hypoglycaemia less than 24 hours prior to dosing, the dosing visit can be rescheduled 1 to 7 days later. Each of the dosing visits can only be rescheduled once.

Prior to study treatment dosing, the patient will be connected to the clamp device for continuous glucose monitoring and the start of the baseline run-in period. Variable IV infusion of either glucose (20% dextrose solution) or insulin (insulin glulisine [Apidra]) will be started to reach a target blood glucose level. Once the target blood glucose level is attained and remains stable, with the predose activities as specified in the Schedule of Activities completed, the patient will receive a dose and undergo the clamp procedure proper. More information on the clamp methodology can be found in Section 9.6.

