### **5.1.2. Outpatient Procedure**

After completing each period, subjects will resume their previous insulin regimen. The investigator will provide instructions for transition back to a normal insulin regimen. Subjects will return for the second dosing period within a 3- to 15-day interval, during which they will have to perform at least 4-point daily SMPG. The basal insulin will have to be discontinued as described previously.

After completing all study treatment dosing and clamp procedures, subjects will resume their former insulin regimen and SMPG routine. A CRU visit for follow-up or early discontinuation should occur at least 14 days after the last dose of study drug.

Abbreviations: CRU = clinical research unit; ED = early discontinuation; SC = subcutaneous; T1DM = type 1 diabetes mellitus.

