below 70 mg/dL (equivalent to blood glucose 63 mg/dL) will not routinely be recorded as hypoglycaemic events during the glucose clamp procedure. However, at the discretion of the investigator, decrease in glucose concentrations may be recorded as a hypoglycaemic event based on clinical concern, or related to technical issues resulting in hypoglycaemia.

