#### **9.4.7.1.1. Severe Hypoglycaemia**

The determination of a hypoglycaemic event as an episode of severe hypoglycaemia, as defined above, is made by the investigator based upon the medical need of the subject to have required assistance and is not predicated on the report of a subject simply having received assistance.

Only severe hypoglycaemic episodes will be reported as AEs. All episodes of severe hypoglycaemia will be reported as SAEs.

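### Does the by-treatment hypoglycaemia table in SAP 9.5.6 need a post-dose window and a rule linking events to products?

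*SAP*

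**What the plan says.** SAP 9.5.6 defines the categories by glucose level, symptoms and need for help, and states: "Each category of hypoglycemic events (defined below) will be listed and summarized by treatment and age group". It sets no start or end time relative to dosing and no rule tying an event to LY900014 or Humalog. The text around it reads as follows.

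- **Clamp lows.** Under Protocol 9.4.7.1, low glucose values "will not routinely be recorded as hypoglycaemic events during the glucose clamp procedure", although the investigator may record one.
- **AE status.** Protocol 9.4.7.1.1: "Only severe hypoglycaemic episodes will be reported as AEs". Every severe episode is also a serious AE.
- **After the clamp.** Protocol 5.1.2: "After completing each period, subjects will resume their previous insulin regimen". Protocol 5.1: "Dosing visits will be separated by a wash-out period of 3 to 15 days". After dose 2, Protocol 5.1.2 says: "A CRU visit for follow-up or early discontinuation should occur at least 14 days after the last dose of study drug".
- **Before dosing.** Protocol 5.1.1 foresees lows in the run-up to a dose; if one occurs "less than 24 hours prior to dosing, the dosing visit can be rescheduled 1 to 7 days later".
- **The AE rule.** SAP 9.5.1: "A non-treatment emergent AE is defined as an AE which starts after informed consent but prior to dosing". A treatment-emergent AE is one that arises or worsens after dosing, with no upper time limit.
- **Table detail.** SAP 3 refers the detailed layout of tables and listings to a separate shell document, which is not among the documents reviewed.

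**The concern.** Each product is given once, at 15 U, and observed for at most 10 hours. Lows in those hours are largely not recorded as events. The subject then spends days or weeks on personal insulin, with self-measured glucose at least four times a day between doses. If every recorded low counts under the most recent product, the table leaves out most lows that occur while the study dose acts and takes in lows on background therapy.

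The start is open as well. A low on the evening before dose 2 belongs to the Period 1 product if events go to the last dose given, and to the Period 2 product if they go by period. Two programmers could tabulate it differently. The AE definitions do not settle this for non-severe lows, because those are not AEs.

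What would be at stake is the description of tolerability in elderly and younger subjects: absolute counts per product could be inflated by own-insulin events, and any real contrast diluted.

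**Working it through.** The plan states no hypoglycaemia rate or window, so there is no figure of its own to reproduce. The check has three parts.

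**1. How much countable time is clamp time?** Inputs: clamp up to 10 h (Protocol 9.6); 3 to 15 days, or 72 to 360 h, after dose 1 (Protocol 5.1); at least 14 days, or 336 h, after dose 2 (Protocol 5.1.2).

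- After dose 1: 10/72 = 13.9% down to 10/360 = 2.8%.
- After dose 2: 10/336 = 3.0% at most.

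So about 86% to 97% of the time, or more with a late follow-up visit, lies outside the clamp. These are shares of time. They cannot be turned into shares of events, because the documents give no event rate and do not say how diary lows reach the case report form.

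**2. Does the open window favour a product?** The intervals differ between periods: 336/72 = 4.67 for a 3-day washout and 336/360 = 0.93 for a 15-day one. That is a contrast of periods, not of products. Let n1 and n2 be the sizes of the two sequences, d the mean days after dose 1 and f the mean days after dose 2, with d and f the same in both sequences in expectation.

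- Product given first in sequence 1: n1 × d + n2 × f.
- The other product: n2 × d + n1 × f.
- Difference: (n1 − n2) × (d − f), which is zero when n1 = n2.

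With 34 completers per age group (Protocol 10.1), an assumed split of 17 and 17, and f = 14:

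- d = 3: 17 × 3 + 17 × 14 = 289 subject-days for each product.
- d = 15: 17 × 15 + 17 × 14 = 493 subject-days for each product.
- Clamp time: 34 × 10/24 = 14.2 subject-days, which is 4.9% of 289 and 2.9% of 493.

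The same symmetry covers lows just before dose 2. Whether they go to the last dose or by period, each product is the Period 1 product for 17 subjects and the Period 2 product for the other 17. Protocol 5.2 gives replacements the sequence of the subject they replace, which helps to keep the split even.

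**3. Would a fixed window repair the table?** Take 24 h after dosing, which always fits a 3-day washout.

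- Hours after the clamp: at least 24 − 10 = 14, and 14/24 = 58%.
- At the end of the clamp the subject receives a meal with prandial insulin, and basal insulin may restart (Protocol 9.6).
- Lows in the other 10 hours are mostly unrecorded.

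The window would shorten the count, but most of its recordable hours would still be own-insulin hours. It would also part from SAP 9.5.1. A severe low on day 5 after dose 1 would be a treatment-emergent serious AE under a product in the AE tables, yet unattributed in the hypoglycaemia table.

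The nocturnal category adds little. Protocol 9.6 allows glucose stabilisation until 1400 hours, so a 10-hour clamp can run to about midnight and overlap bedtime. The category follows the time-of-day definition in Protocol 9.4.7.1 and makes no claim about drug action.

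**The case for a change.** The strongest case for a change is that hypoglycaemia is the first potential risk named in Protocol 3.3, and that safety and tolerability form a secondary objective. Non-severe lows escape both the treatment-emergent definition and the relatedness tables. The SAP takes more care elsewhere: it tabulates injection-site findings and pain categories by timepoint (9.5.7, 9.5.8) and pools antibody results across treatments (9.5.9). A sentence in 9.5.6 would cost almost nothing. That the shells might hold a rule cannot be checked.

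Two parts of this stand. The text does leave the attribution open, and absolute counts per product should not be read as rates caused by one dose.

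The rest does not carry a change. The SAP states no rule that gives a wrong answer; it leaves out a programming convention that analysts set as a matter of course, in the shells or by extending the post-dose logic of 9.5.1. The category with the greatest clinical weight, severe hypoglycaemia, is already under the AE rules. The obvious replacement is not clearly better, for the reasons in part 3 of the working, and any other window length would be a judgement too.

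**Conclusion.** No change to the plan is needed. SAP 9.5.6 leaves a detail unwritten, and analysts can fill it sensibly. The cost of leaving it is noise and possibly inflated absolute counts of non-severe lows in one descriptive table. There is no test on these data, the named safety endpoint is AEs (Protocol 4), and the open window gives no expected advantage to either product. The full listing lets a reader separate pre-dose, clamp and own-insulin events.

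This rests on three assumptions: the two sequences are of about equal size within each age group; the same convention is applied to both products; and event dates and times are captured, which 9.5.6 does not state outright, although it does have the glucose value and any treatment of the event recorded. The share of events arising on own insulin cannot be derived from the documents.
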